In order to specifically address this issue, Elmunzer and colleagues recently evaluated the role of rectal indomethacin in the prevention of PEP in high-risk patients (17). This multicenter, randomized, placebo-controlled, double-blind clinical trial assigned high-risk patients (82% had suspected or confirmed SOD) to receive a single dose (100mg) of rectal indomethacin or placebo (a glycerin suppository) immediately after ERCP. Post-ERCP pancreatitis developed in 27/295 patients (9.2%) in the indomethacin group compared with 52/307 (16.9%) in the placebo group ($p=0.005$). This beneficial effect of indomethacin was seen across all subgroups analyzed. Furthermore, moderate-to-severe pancreatitis rates were significantly lower in the indomethacin group (4.4% vs 8.8%, $p=0.03$). Adverse events were uncommon, as clinically significant bleeding occurred in 4 patients in the indomethacin group and 7 patients in the placebo group ($p=0.72$). Two cases of acute renal failure occurred, both in the placebo group. While confirmatory data would be of interest, indomethacin appears to be the first unequivocally effective pharmacologic agent in the prevention of PEP in high-risk patients. Indeed, anecdotal data currently suggest that indomethacin is being increasingly adopted into widespread clinical use for the prophylaxis of PEP.

While the beneficial effect of indomethacin as demonstrated by Elmunzer et al. (17) represents a major advancement in PEP prevention, pancreatitis rates remain unacceptably high in high-risk patients -- nearly 10% in this study which took place in academic centers with experienced endoscopists. When used as an analgesic or anti-inflammatory agent in the management of patients with arthritis (gout, rheumatoid, ankylosing spondylitis), the recommended maximal daily dose of indomethacin is 200 mg per day, in divided doses (product insert, Merck & Co.). The half-life of this agent is approximately 4.5 hours. Potentially, a higher dose of indomethacin, perhaps leading to a higher peak serum concentration, might further lower PEP rates in high-risk patients. Alternatively, a second dose of the drug might lead to a more sustained effect. We acknowledge that there are no pharmacokinetic data to confirm or substantiate these hypotheses. If either of these phenomena is important in pancreatitis prevention, then a regimen consisting of a higher initial dose followed by a second dose may be hypothesized to be superior.

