While all patients undergoing ERCP may benefit from the protective effect of indomethacin, the incidence of pancreatitis in high-risk patients is such that prevention of PEP in this patient population would lead to the most substantial reduction in morbidity and health care costs. Moreover, the elevated baseline risk of PEP in high-risk patients makes clinical trials in this group more feasible due to more manageable sample sizes.

Our objective is to perform a prospective, randomized, double-blind trial evaluating two different dose regimens of rectal indomethacin in the prevention of PEP. While a single 100 mg dose (the "standard" dose) is effective in high-risk patients (17), the ideal or most efficacious dose regimen is unknown. This study will determine which dose regimen of rectal indomethacin is more effective in preventing post-ERCP pancreatitis. The results will help the research team determine whether there is reason to continue this line of research or whether it would be better to focus on a different area (perhaps use of another class of drugs or a device).

D. Sample size calculation:

An internal audit of high-risk ERCPs at the four tertiary referral centers involved in this clinical trial reveals a PEP rate of approximately 10%, despite the routine use of prophylactic pancreatic duct stent placement (24-26) in appropriate patients and selective use of indomethacin. It is anticipated that the patient characteristics/demographics in this study will be very similar to that of Elmunzer et al. (17), as inclusion and exclusion criteria will be the same (see below). In that study (17), the PEP rate in patients who received indomethacin 100 mg was 9.2%. To achieve a 50% reduction in the rate of PEP (i.e. to 4.6%), with two-sided $\alpha=0.05$ and a power of 0.8, the necessary sample size is 1036. This absolute reduction in incidence

is felt to be clinically relevant and substantial enough to change existing clinical practice.

E. Methodology- Design and procedures

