Included patients are those undergoing ERCP and have:

one of the following:

- 1) Suspected sphincter of Oddi dysfunction, type I or type II
- 2) History of post-ERCP pancreatitis (at least one episode)
- 3) Pancreatic sphincterotomy
- 4) Pre-cut (access) sphincterotomy
- 5) > 8 cannulation attempts of any sphincter
- 6) Pneumatic dilation of intact biliary sphincter
- 7) Ampullectomy
- 8) Assessment for post-sphincterotomy stenosis

or **at least 2** of the following:

- 1) Age < 50 years old and female gender
- 2) History of recurrent pancreatitis (at least 2 episodes)
- 3) ≥3 pancreatic injections, with at least one injection to tail
- 4) Pancreatic acinarization (excluding ventral pancreas of pancreas divisum)

5) Pancreatic brush cytology.

Exclusion criteria:

- 1) Unwillingness or inability to consent for the study
- 2) Age < 18 years
- 3) Intrauterine pregnancy
- 4) Breastfeeding mother
- 5) Standard contraindications to ERCP
- 6) Allergy / hypersensitivity to aspirin or NSAIDs
- 7) Received NSAIDs in prior 7 days (aspirin 325 mg or less OK)
- 8) Renal failure (Cr > 1.4)
- 9) Active or recent (within 4 weeks) gastrointestinal hemorrhage
- 10) Acute pancreatitis (lipase peak) within 72 hours
- 11) Known chronic calcific pancreatitis
- 12) Pancreatic head mass
- 13) Procedure performed on major papilla/ventral pancreatic duct in a patient with pancreas divisum (dorsal duct not attempted or injected)
- 14) ERCP for biliary stent removal or exchange without anticipated pancreatogram
- 15) Subject with prior biliary sphincterotomy now scheduled for repeat biliary therapy without anticipated pancreatogram
- 16) Anticipated inability to follow protocol
- 17) Known active cardiovascular or cerebrovascular disease

Protocol:

Subjects who do not meet any exclusion criteria may be consented for the trial by a clinical research coordinator or one of the investigators. The consent process will occur prior to ERCP in the procedure preparation area. At this time, the objectives of the study as well as the risks and benefits of enrolling will be explained in detail to potential subjects.

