At our institutions, subjects are observed in the recovery area for approximately 4 hours after the termination of the procedure. Patients who develop abdominal pain (or worsening of their baseline abdominal pain) during this observation period are generally admitted to the hospital (for current inpatients, kept in the hospital) in order to exclude procedural complications, including pancreatitis and perforation. The decision to admit the patient or prolong existing hospitalization will be left to the discretion of the endoscopist and clinical service, respectively. Those patients who are hospitalized will have serum amylase and lipase drawn at least once 24 hours after the procedure and subsequently at the discretion of the clinical service. Patients who are discharged uneventfully after ERCP will be contacted by telephone or email within 5 ± 2 days of the procedure by a study team member to evaluate for the development of post-ERCP pancreatitis and other related or unrelated complications. All subjects will also be contacted 30 ± 5 days by telephone or email after the procedure to verify that information about complications has been captured, particularly bleeding which can be delayed after ERCP. Definitions: PEP will be defined per consensus guidelines (27): 1) New or increased abdominal pain that is clinically consistent with a syndrome of acute pancreatitis **and** 2) amylase or lipase $\geq 3x$ the upper limit of normal 24 hours after the procedure **and** 3) Hospitalization (or prolongation of existing hospitalization) for at least 2 days (at least night of ERCP & next night). Mild PEP will be defined as pancreatitis that results in hospitalization (or prolongation of existing hospitalization) for ≤ 3 days. Moderate PEP will be defined as pancreatitis that results in hospitalization (or prolongation of existing hospitalization) for 4-10 days. Severe PEP will be defined as pancreatitis that results in hospitalization (or prolongation of existing hospitalization) for > 10 days, or leads to the development of pancreatic necrosis or pseudocyst, or requires additional endoscopic, percutaneous, or surgical intervention.

Data management:

Patient demographics, risk factors, the procedural elements of the ERCP, and follow-up data will be

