After enrolling 400 patients (37.7% of total enrollment) a BLINDED interim analysis will be conducted by the independent DSMB as follows. For each subject the DSMB will be provided with 1) the subject ID number, 2) whether or not the primary endpoint (post-ERCP pancreatitis) occurred, 3) whether or not a bleeding event occurred, and 4) in which group (high-dose or standard dose regimen) the patient belonged. If $> 66\%$ of the pancreatitis cases or bleeding cases are in a particular group (high-dose or standard dose regimen), the DSMB will break the code to determine whether these events are in the standard 100 mg indomethacin group or high-dose indomethacin group. This value was selected because it represents a 2:1 (double) frequency of an endpoint outcome in one group or another. If either of these events has occurred at this high frequency in one group or another, then the DSMB will decide that the study should be stopped. Even if the DSMB is required to break the code for this above listed purpose, the investigators will never be aware of this information. The DSMB will simply tell the investigators whether or not to continue the study. If during this blinded interim analysis, the DSMB finds that the proportion of the patients with pancreatitis in the higher dose indomethacin group is significantly lower, a formal statistical analysis will be performed and statistical significance will only be declared (and the study terminated) if the two-sided p value is less than 0.005. In this unlikely circumstance, the DSMB will inform the investigators that the study should be terminated for ethical reasons (i.e., it would be unethical to withhold this from high-risk patients).

After enrolling 600 subjects (56.6% of total enrollment) a BLINDED interim analysis will be conducted by the independent DSMB as follows. For each subject the DSMB will be provided with 1) the subject ID number, 2) whether or not the primary endpoint (post-ERCP pancreatitis) occurred, 3) whether or not a bleeding event occurred, and 4) in which group (high-dose or standard dose regimen) the patient belonged. This analysis will be performed because it was a specific request of the DSMB that it be performed to ensure the safety of subjects. Analysis and criteria for stopping the study at this second interim analysis will be the same as those noted above, for the first interim analysis.

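### No section provides for the DSMB to see renal, cardiovascular or other serious events or deaths, and Section F plans no final comparison of any adverse event

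*Combined protocol and SAP*

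**What the plan says.** **Interim content.** Section F itemises what the DSMB receives for each subject at 400 patients. After the subject ID and PEP status come the last two items: "3) whether or not a bleeding event occurred, and 4) in which group (high-dose or standard dose regimen) the patient belonged". The look at 600 patients repeats the same four items and the same stopping criteria. The reason given for that second look is that "it was a specific request of the DSMB that it be performed to ensure the safety of subjects".

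**Final analysis.** Section F plans Fisher tests for PEP and for moderate-to-severe PEP, a multivariable model for PEP, exploratory subgroups, and an analysis of effect heterogeneity by PEP risk. It specifies no between-arm comparison of bleeding or of any other adverse event.

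**Harms recognised elsewhere.** Section E excludes patients with creatinine above 1.4 (criterion 8) and those with "Known active cardiovascular or cerebrovascular disease" (criterion 17). Section C reports from the earlier placebo-controlled trial of a single 100 mg dose: "Two cases of acute renal failure occurred, both in the placebo group".

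**Collection.** Under Section E, patients discharged uneventfully are contacted at about day 5 about pancreatitis and any other complication, related or not. All subjects are contacted at about day 30 "to verify that information about complications has been captured", with bleeding singled out.

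**The concern.** The protocol treats renal and cardiovascular harm as relevant when it selects patients, and it asks about complications of every kind afterwards. The two places where that information would be used, the DSMB listing and the final analysis, leave it out.

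Two decisions are affected. First, Section F lets the board stop early for benefit at p < 0.005, on the ground that withholding the higher regimen would then be unethical. On the stated listing, that benefit-risk judgement would rest on PEP and bleeding alone. Second, the trial could report that the higher regimen prevents pancreatitis without a pre-planned estimate of its cost in harm. The reassurance in Section C concerns one-time or standard doses, and the earlier trial gave a single 100 mg dose. That evidence does not directly cover the two-administration regimen tested here.

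**Working it through.** **1. The plan's own figure.** Section D states: "with two-sided $\alpha=0.05$ and a power of 0.8, the necessary sample size is 1036", for 9.2% vs 4.6%. The pooled formula per arm is n = [1.960·√(2·0.069·0.931) + 0.842·√(0.092·0.908 + 0.046·0.954)]² / 0.046², which rounds up to 476. The continuity correction, (n/4)·[1 + √(1 + 4/(0.046·n))]², raises this to 518 per arm, so 2 × 518 = 1036. The figure is reproduced. The documents do not state the allocation ratio; 1:1 is assumed here, giving about 200, 300 and 518 per arm at the two looks and at the end.

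**2. Dose contrast (Section E, dosing table).** High dose: 150 + 50 = 200 mg. Standard dose: 100 mg. Ratio 2.0.

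**3. Planned use of each event type.**

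| Event | Asked about (Section E) | In DSMB listing | Final between-arm comparison |
|---|---|---|---|
| PEP | yes | yes | yes |
| Bleeding | yes | yes | none stated |
| Acute renal failure | as a complication | none stated | none stated |
| Cardiovascular or cerebrovascular event | as a complication | none stated | none stated |
| Other serious event, death | as a complication | none stated | none stated |

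**4. What zero events would exclude.** The one-sided 95% upper bound is 1 − 0.05^(1/n):
- n = 200: 1.49%
- n = 300: 0.99%
- n = 518: 0.58%

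**5. Expected renal counts.** The documents give no renal rate for the high dose. Section C implies 0/295 on indomethacin 100 mg, for which the same bound is 1 − 0.05^(1/295) = 1.0%. I therefore take an assumed standard-dose range of 0.3% to 1.0%, and assume that it doubles on high dose.

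| Assumed rates, high vs standard | Look 1 (200 per arm) | Look 2 (300 per arm) |
|---|---|---|
| 0.6% vs 0.3% | 1.2 vs 0.6 | 1.8 vs 0.9 |
| 2.0% vs 1.0% | 4 vs 2 | 6 vs 3 |

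**6. Precision of a final table.** Bleeding in the earlier trial was 4/295 = 1.36% on indomethacin. With about 1.4% in each arm, the 95% confidence interval for the risk difference has half-width 1.96·√(2·0.014·0.986/518) = 1.4 percentage points. Exact Fisher power at 518 per arm to detect a doubling is 26% from 1.36%. For assumed base rates of 1%, 0.5% and 0.2% it is 18%, 7% and 0.7%. The table can therefore estimate and describe, but cannot usefully test.

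**The case against.** **The board may see more than the listing.** Section F says what the DSMB will be given at two looks; it does not forbid other reports. No DSMB charter or serious-event procedure is among the documents, and the board was active enough to request a further look. This stands. A reader might infer that these events will never reach the board, but the documents show only that no section provides for it.

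**The second look is not confined to bleeding.** A reader might infer that it protects against nothing else. That is wrong. PEP is in the listing, Section C calls it the most frequent complication of ERCP, and the trigger of more than 66% of cases works in either direction. An excess of pancreatitis on high dose would therefore be caught.

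**Nothing points to a large renal excess.** This also stands. The only renal data are 0/295 on indomethacin and 2/307 on placebo. The exclusions remove patients at higher risk, Section C notes that 200 mg per day in divided doses is the recommended maximum in arthritis, and the FDA granted an IND exemption. These points lower the expected number of events. They do not explain why events that do occur have no stated route to the board or to the final analysis.

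**The data may be thin.** Section E schedules only amylase and lipase, and only for hospitalised patients. No follow-up creatinine is planned, renal failure as an outcome is not defined, and the contacts are by telephone or email. A renal column would hold clinically recognised cases only. This limits what the fix can deliver but does not remove the case for it.

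**Conclusion.** The point holds as a gap in planned reporting and analysis. Both interim listings are fixed to ID, PEP, bleeding and group. No section routes renal, cardiovascular, cerebrovascular or other serious events, or deaths, to the board, and Section F plans no final between-arm comparison of any adverse event. The listing is the stronger half, because it is a stated rule that gives weaker safety monitoring if followed exactly. The missing final table is closer to an omitted detail.

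The size is modest. Over the assumed range, the first look would expect between 1.8 and 6 renal events in both arms together, and the second between 2.7 and 9. Such numbers call for judgement rather than a test. These figures rest on 1:1 allocation and on assumed rates, not on rates in the documents.

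A reader might also infer that the trial collects no harm beyond pancreatitis and bleeding, or that the higher regimen has been shown to be unsafe. The first is contradicted by the day-5 and day-30 contacts in Section E, and the documents contain no evidence for the second. The primary analysis and the sample size are unaffected.

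**What to change.** 1. In Section F, add to the listings at 400 and 600 patients, by coded group: clinically recognised acute renal failure, cardiovascular and cerebrovascular events, other serious adverse events, and deaths. State that the board reviews these by judgement, with no new numeric stopping rule.
2. Add to Section F one descriptive final table of these events and bleeding by randomised arm, with counts, risk differences and 95% confidence intervals.
3. State in the table's footnote that renal events are those clinically recognised, since no follow-up creatinine is scheduled.
4. If a DSMB charter already covers these events, cite it in place of item 1. Item 2 is still needed.

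The cost is a little more data preparation and review at each look and one extra table, drawn from complications already asked about. The sample size, the alpha and patient management do not change.

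### The >66% bleeding rule has no minimum count: at the earlier trial's bleeding rates, equal in both arms, chance alone would stop the trial 46% to 65% of the time as written

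*Combined protocol and SAP*

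**What the plan says.** Section F (Statistical analysis) describes interim looks by the DSMB at 400 and 600 patients. For each patient the DSMB receives the group, whether post-ERCP pancreatitis (PEP) occurred, and "whether or not a bleeding event occurred". The criterion is more than 66% "of the pancreatitis cases or bleeding cases are in a particular group (high-dose or standard dose regimen"). If it is met, "the DSMB will break the code to determine whether these events are in the standard 100 mg indomethacin group or high-dose indomethacin group". The consequence, worded for either event and either group, is mandatory: "then the DSMB will decide that the study should be stopped".

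The only rationale for the threshold is: "This value was selected because it represents a 2:1 (double) frequency of an endpoint outcome in one group or another". At 600 the rule is repeated: "Analysis and criteria for stopping the study at this second interim analysis will be the same as those noted above".

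The p < 0.005 condition in the same section covers only lower pancreatitis in the high-dose group. No count, p-value or confidence limit is attached to bleeding.

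No passage defines a bleeding event. Section E mentions bleeding only as a complication to ask about at the 30-day contact ("particularly bleeding which can be delayed after ERCP"). The only bleeding data are in Section C, from the earlier placebo-controlled trial: "clinically significant bleeding occurred in 4 patients in the indomethacin group and 7 patients in the placebo group", in arms of 295 and 307.

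**The concern.** A share-of-cases rule behaves very differently at different case counts. With about 37 PEP cases at 400 patients (9.2% of 400), a split above 66% is unusual under equal risk. With a handful of bleeds it is ordinary: three bleeds must split 3:0 or 2:1, and both exceed 66%. In the earlier trial, 7 of 11 bleeds (63.6%) fell in one arm. One more in that arm (8 of 12, 66.7%) would have met this rule.

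A trial ended this way settles neither efficacy nor safety.

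The text also leaves three points open:

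- what counts as a bleeding event;
- whether an exact 2:1 split triggers (it is 66.7%, above 66%, yet the threshold is said to represent 2:1);
- whether direction matters (the code is broken to learn which group has the excess, but the stop sentence ignores the answer).

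**Working it through.** **Plan's own figure.** Section D gives no operating characteristic for the stop rule, only the sample size: 9.2% vs 4.6%, two-sided α = 0.05, power 0.80, N = 1036. With mean rate 0.069 and difference 0.046:

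n = [1.960·√(2·0.069·0.931) + 0.842·√(0.092·0.908 + 0.046·0.954)]² / 0.046² = 475.4 per arm.

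With the continuity correction, n/4·[1 + √(1 + 4/(n·0.046))]² = 518 per arm, or 1036 in total. This reproduces the plan.

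**Inputs for the stop rule.**
- Looks at 400 and 600 patients (Section F). 1:1 allocation is assumed because no ratio is stated, giving 200 and then 300 per arm.
- Bleeding rate, assumed equal in both arms: 4/295 = 1.36%, 7/307 = 2.28% (a placebo-arm rate), pooled 11/602 = 1.83%. Section D expects patients very similar to the earlier trial's.
- Expected bleeds: 400 × 1.36% = 5.4 to 400 × 2.28% = 9.1 at the first look; 8.1 to 13.7 at the second.

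**Chance of meeting the rule for a given total.** Under equal risk, the high-dose count X among t bleeds is Binomial(t, 0.5). For t = 6, every split except 3:3 meets the rule: 1 − 20/64 = 68.8%. For t = 9, one arm needs at least 6: 2·(84 + 36 + 9 + 1)/512 = 50.8%.

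| Total bleeds | As written (>66%) | Strictly more than 2:1 |
|---|---|---|
| 3 | 100% | 25.0% |
| 4 | 62.5% | 62.5% |
| 5 | 37.5% | 37.5% |
| 6 | 68.8% | 21.9% |
| 7 | 45.3% | 45.3% |
| 8 | 28.9% | 28.9% |
| 9 | 50.8% | 18.0% |

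**Overall chance of a false stop on bleeding.** Independent Binomial(200, p) counts per arm at 400, plus Binomial(100, p) per arm to 600, enumerated exactly; simulation agrees.

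| Reading | Look | 1.36% | 1.83% | 2.28% |
|---|---|---|---|---|
| As written | at 400 | 56% | 47% | 39% |
| As written | either look | 65% | 54% | 46% |
| Strictly more than 2:1 | either look | 47% | 39% | 33% |
| >66%, high-dose excess only | either look | 33% | 27% | 23% |
| Strictly more than 2:1, high-dose excess only | either look | 23% | 20% | 17% |

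With a broader bleeding definition, at assumed rates of 3%, 4% and 5%, the as-written figures at either look are 35%, 25% and 18%. For contrast, the same >66% rule on PEP at 9.2% in both arms is met by chance 4.3% of the time at 400 and 1.4% at 600, each look taken alone.

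**Ability to detect a real hazard (either look).**

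| True high-dose risk | As written, base 1.36% | As written, base 2.28% | >66%, high-dose only, base 1.36% | >66%, high-dose only, base 2.28% |
|---|---|---|---|---|
| Equal | 65% | 46% | 33% | 23% |
| Doubled | 71% | 66% | 66% | 64% |
| Tripled | 87% | 90% | 86% | 90% |

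**Effect on the efficacy question.** Simulated at 9.2% vs 4.6%, N = 1036, equal bleeding rates, superiority declared at interim p < 0.005 or final two-sided Fisher p < 0.05. The pancreatitis >66% rule is left out. An interim claim takes precedence over a bleeding stop, and a bleeding stop yields no claim.

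| Rule | 1.36% | 2.28% |
|---|---|---|
| No bleeding rule | 81% | 81% |
| As written | 37% | 50% |
| Strictly more than 2:1 | 50% | 59% |
| >66%, high-dose excess only | 59% | 66% |

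**The case against.** The highest figures need two readings at once: that an exact 2:1 split triggers, and that an excess in either arm stops the trial. Section F gives grounds to doubt both. It says the 66% represents 2:1, so it may be a rounded two thirds. It breaks the code to find the direction. It also calls early stopping for lower pancreatitis with the high dose unlikely, yet under the planned effect the pancreatitis split rule in either direction would be met 54% of the time at 400 alone. This stands as an argument that the text is ambiguous. It does not rescue the rule, because the strictest combination still gives 17% to 23% false stops.

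The weak separation of a doubling from no difference is specific to the as-written reading, and is worst at 1.36% (71% against 65%). If only a high-dose excess stops the trial, separation is reasonable (64% to 66% against 23% to 33%). That qualification stands.

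The power figures depend on choices the plan does not make. If a bleeding stop overrides an interim efficacy claim, 37% and 50% become 30% and 45%. If data from a trial stopped for bleeding were tested at 0.05, they become 54% and 62%, but Section F offers no support for that test. The precedence used here favours the plan.

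The bleeding rate is an assumption resting on 11 events, and a wider definition lowers the false-stop chance. A sensitive safety trigger is also a legitimate aim. That supports keeping the split as a trigger for review, but not as a mandatory stop.

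**Conclusion.** The concern holds. The absence of any minimum count or allowance for chance is plain in the text. Followed as written, the rule gives the high false-stop rates tabulated above. The exact percentage rests on the earlier trial's bleeding rates applying equally to both arms, on 1:1 allocation, on how the threshold and direction are read, and on the stop being binding, as the wording says. If the DSMB kept discretion, these would be chances of meeting the criterion rather than of stopping. Across the readings the range is 17% to 65% at the earlier trial's rates, so none brings the rule to an acceptable level. It must be corrected before the interim looks are run.

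**What to change.** In Section F, and in the DSMB instructions:

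1. Make the >66% bleeding split a trigger for unblinded DSMB review of bleeding counts by arm. Report with it the exact binomial probability of a split at least that uneven for the observed total.
2. Replace the automatic stop with an exact, count-based boundary set in advance by the DSMB, stating its direction and its false-stop probability over both looks.
3. In the same paragraph, define a bleeding event and state whether an exact 2:1 split meets the review trigger.

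The cost is wording in Section F and the DSMB instructions, plus DSMB agreement; the DSMB itself asked for the second look. The real trade-off is that judgement replaces an automatic rule, and an exact boundary stops automatically less often for a true hazard. As an illustration only, a one-sided exact binomial p ≤ 0.05 at each look gives 3% to 4% false stops over both looks at 1.36% to 2.28%. It detects a doubling 25% to 41% of the time and a tripling 61% to 83%. Keeping the split as a review trigger retains its sensitivity, because every case that meets it still reaches the DSMB unblinded.

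### The interim bleeding rule breaks the code to learn which regimen has the excess, then requires a stop whichever it is, so a chance excess on the 100 mg reference regimen would end the trial

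*Combined protocol and SAP*

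**What the plan says.** The rule is in Section F (Statistical analysis) of the combined protocol and SAP, in the paragraph on the look at 400 patients. If more than 66% "of the pancreatitis cases or bleeding cases are in a particular group (high-dose or standard dose regimen), the DSMB will break the code". The purpose of the code break is "to determine whether these events are in the standard 100 mg indomethacin group or high-dose indomethacin group". The threshold was chosen because "it represents a 2:1 (double) frequency of an endpoint outcome in one group or another". The consequence comes next: when either event is that frequent "in one group or another, then the DSMB will decide that the study should be stopped".

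The paragraph on the 600-patient look adds no direction: "Analysis and criteria for stopping the study at this second interim analysis will be the same as those noted above". The only provision in Section F that depends on direction concerns pancreatitis. If pancreatitis is lower on the high dose, a formal test is done and significance needs two-sided p < 0.005. Bleeding has no such provision. No minimum number of bleeding cases is given, and Section F does not define a bleeding event.

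**The concern.** The code-break sentence suggests that the identity of the group matters. The next sentence gives the same result for either group. For bleeding, the two directions carry different information. An excess on the high dose is a safety signal against the regimen under test. An excess on 100 mg, which Section C calls the standard dose and which H1 and H2 use as the comparator, is not evidence against the high dose.

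A DSMB that follows the text would nevertheless have to end the trial at 400 or 600 of 1036 patients. The comparison of pancreatitis rates would then rest on much less power than planned.

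**Working it through.** **Inputs.** Looks at 400 and 600 patients, trigger above 66%, in either direction (Section F). Bleeding in the earlier placebo-controlled indomethacin trial described in Section C: 4/295 = 1.36% on 100 mg and 7/307 = 2.28% on placebo, pooled 11/602 = 1.83%. Pancreatitis 9.2% vs 4.6%, two-sided alpha 0.05, power 0.80, N = 1036 (Section D). Final test: Fisher's exact (Section F).

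**Assumptions.** 1:1 allocation (200 per arm, then 300), cumulative data, complete bleeding follow-up at each look.

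**The plan's sample size.** With d = 0.046 and mean rate 0.069, n = [1.960·√(2·0.069·0.931) + 0.842·√(0.092·0.908 + 0.046·0.954)]² / d² ≈ 475.4. The continuity correction (n/4)·[1 + √(1 + 4/(n·d))]² gives 518 per arm, 1036 in total. This matches Section D and supports the 1:1 assumption.

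**How few cases are involved.** Expected bleeding cases at 400 patients: 400 × 0.0136 = 5.4 to 400 × 0.0228 = 9.1. Splits of 4:1, 4:2 or 5:2 exceed 66%. Their two-sided Fisher p-values at 200 per arm are 0.37, 0.69 and 0.45.

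**Probability of a bleeding stop.** S and H are binomial bleeding counts on the standard and high dose. A look stops for a standard-dose excess if S/(S+H) > 0.66 and for a high-dose excess if H/(S+H) > 0.66. Two-look figures come from 1,000,000 simulated trials. With equal true bleeding in both arms:

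| Bleeding rate | Standard-dose excess, look 1 | Standard-dose excess, both looks | Either direction, both looks | Rule limited to high-dose excess, both looks |
|---|---|---|---|---|
| 1.36% | 0.28 | 0.32 | 0.65 | 0.33 |
| 1.83% | 0.23 | 0.27 | 0.54 | 0.27 |
| 2.28% | 0.20 | 0.23 | 0.46 | 0.23 |

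Outside that range, the both-looks probability for a standard-dose excess is 0.37 at 1%, 0.18 at 3% and 0.09 at 5%.

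**How much is due to the cut-off itself.** At 1.36% / 1.83% / 2.28%, the standard-dose stop over both looks becomes:
- with at least 10 cases required: 0.05 / 0.10 / 0.13;
- with Fisher p < 0.05 required in addition to the 66% share: 0.012 / 0.015 / 0.018.

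**If the high dose does raise bleeding.** Over the same standard-dose rates, the stop for a standard-dose excess is 0.135 to 0.057 for a 1.5-fold increase and 0.051 to 0.012 for a doubling.

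**Detection of harm.** If the high dose doubles bleeding, the chance of stopping for a high-dose excess is 0.66 / 0.65 / 0.64, both as written and with the rule limited to that direction.

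**What a stop costs.** Fisher power at 0.05 for 9.2% vs 4.6% is 0.81 at 1036 patients, 0.37 at 400 and 0.55 at 600.

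**The case against.** Four arguments have weight.

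*The size comes largely from another defect.* This stands in good part. The 0.32 to 0.23 reflects a share threshold applied to a handful of cases. With a minimum count or a significance requirement, the part due to direction alone is far smaller.

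*The repair leaves other stops in place.* This also stands. A rule limited to high-dose excess still stops a trial with no bleeding difference with probability 0.33 to 0.23. The same wording covers pancreatitis: under 9.2% vs 4.6%, that trigger alone fires at either look with probability 0.63. Treating the two triggers as independent, the chance of passing both looks on both rises from 0.13–0.20 to 0.25–0.28.

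*A symmetric rule between two active regimens can be defended.* Partly. If 100 mg truly carried twice the bleeding, continued randomisation to it would be a safety question. A reader might infer that a stop in this direction protects nobody; the documents do not support that. They support only that such an excess is no signal against the high dose and that the plan gives no reason for making the stop automatic.

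*The DSMB would use judgement.* Breaking the code suggests that this may have been intended, but the stop sentence leaves no discretion. Unwritten intent does not resolve the conflict between the sentences. A reader might also infer that the code break has no function at all. That is too strong, since the p < 0.005 provision for pancreatitis needs the direction. The point is confined to bleeding.

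**Conclusion.** The point holds as a should-fix. For bleeding, Section F obtains the direction and then ignores it, at both looks. Under equal bleeding of 1.36% to 2.28%, 1:1 allocation and complete follow-up, the literal rule ends the trial for a standard-dose excess with probability 0.32 to 0.23.

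That figure should not be read as the effect of direction alone, because much of it arises from the missing minimum count. It also depends on the assumed rates, which come from clinically significant bleeding in the earlier trial (the upper one from its placebo arm), whereas Section F counts bleeding events without defining them. A broader definition would give more cases and a lower probability.

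A reader might infer that such a stop costs the trial its answer. The documents support a loss of power, to 0.37 or 0.55, and no more than that.

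**What to change.** The sponsor and DSMB should reconcile the code-break sentence with the mandatory-stop sentence in Section F, for both looks, so that the automatic bleeding stop depends on direction. It would apply to an excess in the high-dose group. An excess in the standard-dose group would go to the DSMB for review and would not by itself force termination.

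The cost is one sentence in Section F and a matching line in the DSMB instructions, with no extra patients or data. The downside is small: a real bleeding excess on the standard dose would no longer stop the trial automatically, though the DSMB would still see it and could act.

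This change does not repair the lack of a minimum count behind the 66% cut-off, or the pancreatitis trigger, which is also non-directional and sits beside the p < 0.005 rule. Both should be reconciled in the same revision.
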